The cognitive reorientation intervention we have developed and pilot tested is a simple but potentially powerful strategy to provide structured information in a familiar voice to patients on a regular basis. Because the intervention has a strong nursing care focus, it has the potential to affect delirium in ways that are distinct from but synergistic with medical care, which has focused primarily on pharmacologic management of delirium. The FAVoR intervention we propose in this project holds promise for reducing delirium in critically ill adults, improving sleep in the ICU, and secondarily benefitting cognitive function post-ICU.

We will accomplish the objectives using a prospective, randomized, experimental design to achieve robust and unbiased results. Subjects (n=182) will be randomly assigned within 48 hours of ICU admission and intubation to one of two groups. In the intervention group, scripted audio messages recorded by the patient's family (FAVoR) will be played for the patient at hourly intervals during daytime hours. These messages will be personalized, delivered automatically, and provide information about the ICU environment. Subjects in the control group will not receive recorded audio FAVoR messages. The FAVoR intervention, a standardized protocol developed and tested in preliminary work, will be delivered by audio recording for 5 consecutive days (120 hours), or until ICU discharge if discharge occurs within the first 5 days. The number of episodes of delirium during ICU stay is the primary outcome measure. We will also collect data at 1 month and 6 months following ICU stay for secondary aim 3. A model of the study is presented in Figure 1.

IRB Study Number: 20170771, Version #1.8, Date: 03/10/21, PI: [name]

[figure not shown]
Preliminary Studies

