	Drug type and cumulative sedative dose	**	**	**	**	**	***	***
	APACHE IV STOP-BANG SOFA			**	*		***	***
	Age, sex, race/ethnicity		*		**	**		
Patient-reported Health Status	PROMIS Global Health					*	***	***
Patient-reported Sleep Quality	PROMIS-SD PROMIS-SRI					*	***	***
Patient-reported Cognitive Function	PROMIS-CF PROMIS-CFA					*	***	***
Cognitive Function	NIH Toolbox Cognition Battery					*	*	*

Note:

* = Data collection in person (measures shaded in grey are temporarily paused)

** = Data collection from the electronic medical record

*** = Data collection via telephone or video conference visit (measures highlighted in yellow are telephone- or video-collected substitutes for in-person visits)

We plan to review approximately 350 medical records in order to achieve our sample size of 182 enrollments during the 4-year study. The data collection schedule is shown in Table 2.

IRB Study Number: 20170771, Version #1.8, Date: 03/10/21, PI: [name]

Table 2. Study Timeline

Activity	Year	Year 1			Year 2			Year 3			Year 4		
	Months	1-4	5-8	9-12	1-4	5-8	9-12	1-4	5-8	9-12	1-4	5-8	9-12
Hire/train personnel													
Database refinement													
Subject recruitment and enrollment													
Subject 1 and 6 month follow up													
Data collection													
Data management													
Analysis of final results													
Final results manuscript													
Final grant report													

8. Study Endpoints

Primary Endpoint. To test the effect of the Family Automated Voice Reorientation (FAVoR) intervention on delirium in critically ill, mechanically ventilated adults during hospitalization in the ICU, we plan for 95% power respectively to detect an effect size (W) of 0.35 using a 2 degrees of freedom Chi-Square Test with a significance level (alpha) of 0.05.

Secondary Endpoint. The recently completed BRAIN-ICU descriptive study of ICU survivors reported a 43% attrition from the inpatient sample to a 12 month follow up time point.¹⁸ Given that a secondary aim of the proposed project plans 1month and 6 months post-hospital discharge follow up, we conservatively planned for a 40% attrition rate, which is a sample size of 182 total (91 in each group).

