- 1) **Intervention Group:** Subjects in the intervention group will receive personalized digitally recorded reorientation messages administered for up to 2 minutes every hour over an 8-hour daytime period (beginning at 9 am daily) recorded in the voice of a family member. Subjects in the intervention group will continue to receive the intervention for up to a total of 5 days (120 hours), or until ICU discharge if ICU discharge occurs within the first 5 days. Since in the ICU setting delirium has a mean onset of 2.6 days (S.D. +/- 1.7), and a mean duration of 3.4 +/- 1.9 days,⁴⁹ a 5-day period for the study intervention is appropriate and includes the period prior to delirium onset as well as when delirium has been shown to occur most frequently.
- 2) **Control Group:** The control group will consist of usual care, and will not receive audio reorientation messages. Subjects will remain in the study for five days or until ICU discharge if discharged before five days.

Subjects in both groups will be reoriented by care providers as part of usual care practices. Data will be collected from the medical record daily. Both groups (intervention and control) will undergo longitudinal cognitive and patient-reported health status evaluations concurrently with 24-hour sleep profiler-polysomnography and actigraphy at three different points in time. The first time point is inpatient, at least 24 hours after ICU discharge, then outpatient with two home visit data collection events at 1 month and 6 months post hospital discharge.

Description of Intervention. The FAVoR intervention includes a set of 8 recorded messages which were developed in preliminary study 1, and were tested and refined in preliminary study 2. Based on the feasibility data (preliminary study 2) each message is scripted, is no longer than

IRB Study Number: 20170771, Version #1.8, Date: 03/10/21, PI: [name]

2 minutes long, is a personal message using the subject's name, uses simple terms, and is written at a 5th grade reading level. Messages include information about the critical care environment, the visual and auditory stimuli to be expected, and the availability of providers and family. The messages call the patient by name (preferred name as recommended by the patient's family); we believe the use of the patient's name may create greater attention to the message.

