3. SP-PSG (substituted by PROMIS-SD and PROMIS-SRI)
4. NIH Toolbox Cognition Battery (substituted by PROMIS-CF and PROMIS-CFA)

Delirium. The primary outcome measure for this project is delirium free days. We will quantify delirium using the Confusion Assessment Method for the ICU (CAM-ICU).⁴⁵ CAM-ICU scores for each subject will be obtained by study personnel twice daily at 9 am and 4 pm (coinciding with the schedule for initiation and conclusion of messages each day in the FAVoR intervention group, and at identical times for the control group). CAM-ICU scores will also be recorded at the same times for two days following the completion of the intervention period. The Confusion Assessment Method (CAM) will be used during study visits after transfer from the ICU (post ICU, 1 month, and 6 month follow up periods) for comparison.

We will also collect documentation by providers in the medical record of episodes of delirium occurring outside of the CAM-ICU data collection conducted by research personnel. Only days without any instances of delirium will be counted as delirium free days. The CAM-ICU is recognized in the Clinical Practice Guidelines for the Management of Pain, Agitation, and Delirium in Adult Patients in the Intensive Care Unit as a valid, reliable, and feasible tool to detect delirium in ICU patients³ with pooled sensitivity of 75.5% and specificity of 95.8%.⁵⁰

Sleep/Activity. Sleep patterns in the critically ill are highly disorganized, with fragmentation, a predominance of light sleep, and reduction in deep sleep and rapid eye movements.⁸ We will use the FDA approved Sleep Profiler system (Advanced Brain Monitoring, Carlsbad, CA) to obtain continuous polysomnography data (SPPSG). The Sleep Profiler has been successfully utilized in mechanically ventilated and sedated patients and provides three frontopolar electroencephalographic (EEG) signals (AF7/AF8, AF7/Fpz and AF8/Fpz).⁵¹⁻⁵⁴

A wrist actigraph (ActiWatch Spectrum, Philips Respironics, Bend, OR) will be placed on the wrist to measure patient activity and ambient light levels. We have extensive experience with

IRB Study Number: 20170771, Version #1.8, Date: 03/10/21, PI: [name]

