There will be two parts of the data analysis: Part I: A traditional statistical data analysis for randomized controlled trials for the Primary Specific Aim, and Part II: Pathway analytic model analyses to address the secondary aims. [name] will work closely with the Data Manager to perform all the planned data analyses for this study.

Part I: We will follow the research and regulatory guidelines for statistical analysis of clinical trials including the ICH Guideline⁷⁷ and the CONSORT guidelines⁷⁸. First, descriptive statistics will be performed to describe and compare the characteristics of the intervention and the control groups. Descriptive statistics will be reported as means +/- standard deviation for continuous variables and as frequencies and percentages for categorical variables. Shapes of the data distributions, missing data and outliers will be examined by both graphics and statistical tests. Any data issues identified will be discussed with the PI and other investigators and addressed before formal data analysis. For example, skewed variables may be transformed so that their distributions are close to the Normal Distribution. Outliers may be excluded or included in two separate analyses. Missing data may be imputed or handled by other missing data techniques. Distributions of continuous variables and categorical variables will be compared between the intervention and the control group by using the t-test or Wilcoxon rank sum test and the Chisquare test, respectively. Any baseline covariate that is differentially distributed in the two groups will be adjusted in the subsequent analysis for testing the intervention effect. Assuming the randomization produces well balanced intervention and control groups, a Chi-square test for a 2x2 table with the number of delirium free days and the treatment assignment will be performed to test the primary hypothesis. If there are unbalanced covariates, then covariance adjustment will be performed by using logistic regression that includes both the treatment assignment and the unbalanced covariates. If there are missing values in the primary outcome, then multiple imputation will be performed using SAS PROC MI for missing at random (MAR) data.^{79,80} Sensitivity analysis for potentially not missing at random data will be performed using the Yau and Little⁸¹ Intent-to-Treat Analysis for Longitudinal Studies with Dropouts.

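### The primary outcome is named two ways, its 2x2 test has no patient-level split and does not match the 2-df sample size, and the counting window and scoring of unobserved days are not stated

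*Combined protocol and SAP*

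**What the plan says.** **Outcome.** Section 4 (Background, the design summary before Preliminary Studies) states: "The number of episodes of delirium during ICU stay is the primary outcome measure". Section 9 (Key Variables, Delirium) states: "The primary outcome measure for this project is delirium free days". Both are current text.

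**Test.** Section 10 (Data Analysis Plan, Part I) says that "a Chi-square test for a 2x2 table with the number of delirium free days and the treatment assignment will be performed". If baseline covariates are unbalanced, "covariance adjustment will be performed by using logistic regression that includes both the treatment assignment and the unbalanced covariates".

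**Sample size.** Section 8 plans 95% power for w = 0.35 at alpha 0.05, "using a 2 degrees of freedom Chi-Square Test". With 40% attrition it arrives at 182 patients, 91 per group. The attrition figure is argued from loss at long-term follow-up.

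**Day rule and timing.** Section 9 schedules CAM-ICU at 9 am and 4 pm, adds delirium charted by providers, and states: "Only days without any instances of delirium will be counted as delirium free days". It also says: "CAM-ICU scores will also be recorded at the same times for two days following the completion of the intervention period". Table 1 in Section 7 shows these as ICU days 6-7. For controls, Section 9 says: "Subjects will remain in the study for five days or until ICU discharge if discharged before five days".

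**Truncated data.** Section 12 stops collection when a patient's circumstances change or consent is withdrawn, and uses what was collected to that point. Sections 8 and 13 cut the in-hospital data after a second vital-sign fluctuation of 20% or more during a recorded message. Section 10 plans multiple imputation under MAR for missing primary outcomes, with a sensitivity analysis for data not missing at random.

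**The concern.** A confirmatory test needs one outcome per patient, a period over which it is measured, and a test that fits it. Here each is at least partly open.

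The two named outcomes are not interchangeable. One long episode leaves few free days, while several one-day episodes can leave more. A count of free days does not fill a 2x2 table without a split, and none is given. The sample size is calculated for a test with different degrees of freedom from the planned one. The count could run over 5 days, 7 days or the whole ICU stay, and days that nobody observed have no score.

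These choices would have to be made later, possibly with data in view, and the same patients could then give different primary results. One gap is also not neutral between arms: the vital-sign data cut is triggered by the recorded message, so only the intervention arm can lose days to it.

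**Working it through.** **1. Degrees of freedom.** A table of r rows and c columns has (r - 1)(c - 1) df. Two arms by yes/no gives 1. Two df would need two arms by three outcome levels, or three groups by yes/no. The trial has two arms, and no section defines three outcome levels.

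**2. Sample size.** Inputs from Section 8: w = 0.35, alpha 0.05, power 95%. The noncentrality parameter is lambda = N x w^2 = 0.1225 N. Power is the probability that a noncentral chi-square variable exceeds the 5% critical value (3.84 for 1 df, 5.99 for 2 df).

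| | 1 df | 2 df |
|---|---|---|
| lambda for 95% power | 12.99 | 15.44 |
| N = lambda / 0.1225 | 106.1, so 107 | 126.1, so 127 |
| Power at N = 109 | 95.5% | 91.6% |
| Power at N = 182 | 99.7% | 99.2% |

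The 109 is 182 x 0.6 = 109.2, that is, 182 less the 40% planned for follow-up. That loss need not apply to an outcome measured in the ICU.

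**3. Can 182 be reproduced?** The number before inflation is not stated. From 2 df, 127 x 1.4 = 177.8, so 178; 130 x 1.4 = 182 exactly, with 95.6% power at 130. Dividing by 0.6 instead gives 127 / 0.6 = 211.7, so 212. From 1 df, 107 / 0.6 = 178.3, so 179. More than one route ends at or near 182, so the documents do not show which was used.

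**4. The 2x2 table.** Two readings are possible.

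- *One row of data per patient.* A split of the count is needed, for both the chi-square and the logistic regression. None is given.
- *One row of data per patient-day.* The day rule makes each day yes or no, so the table can be filled. The pilot in Section 4 is consistent with this. Mean delirious days were 0.2 and 0.9, with 10 patients per group over three days. That gives 2 of 30 and 9 of 30 patient-days if every day was observed. The expected counts are 5.5 delirious and 24.5 free days per group, so the continuity-corrected chi-square is (3.5 - 0.5)^2 x (2/5.5 + 2/24.5) = 4.007, p = 0.0453. The pilot reports p = 0.0450. This is suggestive, not proof. On this reading, days of one patient are treated as independent although they are correlated, so the p-value and standard errors are invalid. The 107 and 127 above count independent patients and would not apply.

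**5. Counting window.** CAM-ICU runs over ICU days 1-5 plus two more days, controls remain in the study for five days, and Section 4 refers to the whole ICU stay, but for episodes. No section says which period the free days cover. Section 7 starts data collection after consent. Section 9 (Inpatient) starts control monitoring devices as soon as feasible after consent, while the intervention may wait for the family recording until the next morning. Day 1 of the delirium count is not fixed for either arm.

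**6. Unobserved days.** No score is given for days after ICU discharge, after death, after collection stops, after the data cut, or without a completed CAM-ICU. The imputation plan does not say which of these are missing and which lie outside the count. Read literally, the day rule can count as free a day with no assessment and no charted delirium.

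**7. Length of stay.** Suppose all ICU days to day 7 are counted raw. A patient never delirious and discharged after day 3 scores 3. A patient delirious for 3 days of a 7-day stay scores 7 - 3 = 4. If only days 1-5 count and the delirium falls on days 1-3, the scores are 3 and 5 - 3 = 2, and the reversal disappears.

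**The case against.** Several parts of the opposing case stand.

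- Section 9 and Section 10 agree on delirium-free days. Episodes appear as the primary outcome only in the Background, so that conflict can be settled by a short correction.
- A reader might infer that the plan has no day-level rules. It does: Section 9 gives the main rule, the assessment times and the use of charted delirium. Only the rules for unobserved days and the window are absent.
- A reader might infer that the primary test cannot be carried out at all. The patient-day reading can be carried out, and the pilot's p-value hints at it. The fault there is different: correlated days analysed as independent.
- The 2 df may be left over from the three-group pilot. The documents do not say, and the trial now has two arms.
- A reader might infer that the trial is underpowered. For the 2x2 test at w = 0.35 it is not. Only a 2-df test with 40% of patients lost falls below the stated 95%, at 91.6%.
- The length-of-stay reversal needs days 6-7 to count, which is not stated. Its average effect depends on ICU stays and on why delirious patients stay longer, and the documents do not settle either.

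What remains is that the outcome, unit of analysis, window and scoring of unobserved days are not fixed by any combination of sections.

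**Conclusion.** The concern holds as a fault of specification that should be corrected before analysis. Followed as written, the plan leads either to a patient-level test with no defined split, or to a patient-day test with invalid error bars. The sample-size statement belongs to a test with different degrees of freedom.

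The size that can be stated is 127 against 107 evaluable patients, a gap of 20. At 109 evaluable patients, power is 91.6% for 2 df and 95.5% for 1 df; at 182 it exceeds 99% for both. These figures assume independent patients, w = 0.35 and alpha 0.05. The mismatch alone therefore costs the 2x2 test nothing that matters. The weight of the point lies in the open choices and in a data cut that only one arm can trigger.

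That a longer stay can score better than a short delirium-free one is shown for a raw count to day 7 only. The documents give no basis for saying how much it would change the result.

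**What to change.** 1. Make Section 4 agree with Sections 9 and 10 on one primary outcome. Make the other secondary and define an episode.
2. Make the patient the unit of analysis and match the test to the outcome. Either use a patient-level yes/no outcome, for example any versus no in-ICU delirium over a stated window, which keeps the 2x2 chi-square and logistic regression. Or use delirium-free days per patient with the Wilcoxon rank-sum test (already named in Section 10 for group comparisons) and an adjusted model that suits a count or ordered outcome.
3. State one counting window that starts at the same point in both arms.
4. State how days after ICU discharge, death, withdrawal and the data cut enter the outcome. Reconcile Section 12, which keeps data collected before withdrawal, with Section 26, which destroys the data forms. Treat an ICU day with no completed CAM-ICU and no other assessment as missing under Section 10, not as delirium-free.
5. Restate Section 8 for the chosen test: 1 df and 107 evaluable at w = 0.35 for a 2x2 table, or a separate basis for Wilcoxon.

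The cost is wording in Sections 4, 8, 9 and 10, the reconciliation of Sections 12 and 26, and identification of the days without an assessment. With the 2x2 option, 182 remains sufficient at w = 0.35. There are trade-offs. Any versus none ignores how long delirium lasts. A fixed window that runs past ICU discharge relies on weaker detection there: chart entries and the CAM at 24-72 hours. The choice between the two options is the sponsor's.

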Because the intervention scripts have been developed, IRB approved, and pilot tested in English and Spanish, patients who do not speak either English or Spanish, as identified by self or their family, will be excluded.

Inclusion of Adults Unable to Consent

In our experience in conducting clinical research in the critical care areas, we have found that potential subjects who are mechanically ventilated are generally sedated to some degree. In addition, since use of mechanical ventilation primarily occurs during periods of patient instability, the use of sedation at these times is extensive and compromises patient's ability to communicate effectively which is compounded by the presence of the endotracheal tube. As a result, we have always found it appropriate to contact the legally authorized representative for consent. However, there may be rare occurrences when potential subjects are adequately oriented and lucid to be able to provide informed consent. Therefore, we will use the 2-step procedure described by Fan et al.⁷⁶ to determine the patient's ability to provide informed consent. Step 1 is objective evaluation with the Richmond Agitation-Sedation Scale (RASS) and the Confusion Assessment Method for Intensive Care Unit (CAM-ICU). Patients who score -1, 0, +1 on the RASS indicating drowsy, alert, or restless respectively and are not delirious (CAM-ICU = No) will move to Step 2. Step 2 is assessment for competency using the MacArthur Competence Assessment Tool for Clinical Research: MacCAT-CR that evaluates all four capacity domains for consent (understanding, appreciation, reasoning, expression of a choice). Evaluation of Step 1 requires approximately 2-3 minutes, Step 2 requires approximately 15 minutes. Fan et al.⁷⁶ found in consent evaluations of 150 ICU patients that 89% were sedated/delirious, and unable to provide consent; our experience in previous research is similar. Therefore, we expect that few potential subjects will move to Step 2 while critically ill and mechanically ventilated. The LAR will be contacted for those who fail Step 1 or Step 2.

IRB Study Number: 20170771, Version #1.8, Date: 03/10/21, PI: [name]

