2. If the family member is found not to be available at bedside, the Project Director or RA will contact healthcare proxy or family member using the phone number found in patient's medical record, and will follow the Recruitment Script to speak with the family member regarding interest in study participation.
 - a. In our experience, finding family members at the bedside during the eligibility window of 48 hours from admission or intubation has been a unique challenge in Miami hospitals. Many family members avoid staying in the hospital setting and visit infrequently or for short periods of time; some of the hospital units we recruit from have strict limitations on visitation time (15 minutes at a time, for example). Placing a call directly to family members would allow for family to be invited directly to discuss possible study participation.
3. If family is present at the bedside, the Project Director or RA will follow the Recruitment Script to address both the potential subject and family member regarding interest in study participation.
4. If the patient does not have a family member available and/or willing to record the scripted reorientation messages, the patient is not eligible for study enrollment. No identifying information will be retained.
5. If the patient has a family member available and willing to record the scripted reorientation messages, then the Project Director or RA will move on to the enrollment process.

Enrollment process:

2. The potential subject's capacity to consent will be determined (see section 18. Consent Process).
 - a. In our experience, potential subjects who are critically ill, especially during the first 48 hours of intubation, are always sedated to some degree, and their ability to communicate effectively may be compromised by endotracheal intubation; in

IRB Study Number: 20170771, Version #1.8, Date: 03/10/21, PI: [name]

these cases, consent has been obtained from the legally authorized representative (LAR).

3. If the potential subject or their LAR is not interested in consenting to participate in the study, no identifying information will be retained.
4. If the LAR is contacted by phone or HIPAA compliant Zoom:
 - a. Review of the consent forms will be completed over the phone or by Zoom by the Project Director or RAs, as is done in person.
 - b. Verbal consent will be obtained over the phone or by Zoom.
 - c. Waiver of wet signature will be documented by the person obtaining consent.

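### The counting rule for delirium free days does not separate a tested-negative day from a day when the patient could not be tested, so unequal arousal between arms would bias the primary comparison

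*Combined protocol and SAP*

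**What the plan says.** In section 9 (Key Variables and Their Measurement, Delirium) the plan states: "The primary outcome measure for this project is delirium free days". Study staff do the CAM-ICU "twice daily at 9 am and 4 pm", and "CAM-ICU scores will also be recorded at the same times for two days following the completion of the intervention period". Delirium episodes that providers document in the medical record are also collected. The only counting rule is "Only days without any instances of delirium will be counted as delirium free days".

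The documents contain no code for a CAM-ICU that cannot be completed and no rule for a day spent in coma or deep sedation. Table 1 lists no arousal score beside the CAM-ICU. The RASS appears only in the consent-capacity procedure (sections 5, 15 and 26), where it is a criterion separate from the CAM-ICU result. Coma is not an exclusion in section 5, and neuro ICUs recruit (sections 17 and 20).

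On sedation, section 5 says that "potential subjects who are mechanically ventilated are generally sedated to some degree" and that "the use of sedation at these times is extensive and compromises patient's ability to communicate effectively". The enrollment process in section 20 says that potential subjects, "especially during the first 48 hours of intubation, are always sedated to some degree".

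Section 10 (Data Analysis Plan, Part I) plans multiple imputation under missing at random for missing primary-outcome values, plus a sensitivity analysis for data not missing at random. It does not say that an untestable day is missing.

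**The concern.** A patient who cannot be roused at either assessment gives no positive CAM-ICU. With no chart entry of delirium, that day has no instance of delirium and passes the only stated rule. A patient in coma for a week can then score the same as one who is awake and oriented, and better than one who wakes into delirium.

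This matters most if the arms differ in arousal. Section 4 makes that plausible: it says recorded family messages may benefit consciousness, and it cites a 40-patient trial in comatose patients with better GCS scores in the message group. If FAVoR makes patients testable sooner, it also exposes them to positive results that unarousable controls cannot produce. If one arm happens to be more deeply sedated, that arm gains apparent delirium free days for that reason alone.

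The other wording of the primary outcome, in section 4 ("The number of episodes of delirium during ICU stay is the primary outcome measure"), shares the weakness, because an untestable day adds no episode. The disagreement between the two wordings is a separate matter.

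**Working it through.** **Inputs from the documents.** Two assessments a day over 5 + 2 = 7 days (section 9). Planned effect size W = 0.35 and 91 per arm (section 8). Pilot mean delirium days 0.2 (family voice) and 0.9 (control) (section 4, preliminary study 2).

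**Assumptions.** The plan gives no rate of untestable days, so there is no figure of its own to reproduce. Let c be the share of untestable days and d the delirium risk on a testable day, with subscript 0 for control and 1 for FAVoR. All c and d values below are assumed. That an unarousable patient cannot score positive on the CAM-ICU is also an assumption; the documents do not state it.

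**Formulas, per day.**
- Free under the stated rule: 1 − (1 − c)d
- Free of both delirium and coma: (1 − c)(1 − d)
- The stated rule shows FAVoR worse when (1 − c1)d1 > (1 − c0)d0, that is, when d1/d0 > (1 − c0)/(1 − c1)

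**Main example.** c0 = 0.40, c1 = 0.20, d0 = 0.60, d1 = 0.50.
- Stated rule: control 7 × (1 − 0.60 × 0.60) = 4.48; FAVoR 7 × (1 − 0.80 × 0.50) = 4.20; difference −0.28 day.
- Delirium- and coma-free: 7 × 0.60 × 0.40 = 1.68; 7 × 0.80 × 0.50 = 2.80; difference +1.12 days.
- Check: d1/d0 = 0.83 exceeds the break-even 0.60/0.80 = 0.75, so the sign reverses.

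**Other assumed cases** (control/FAVoR; differences are FAVoR minus control, over 7 days):

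| c0/c1 | d0/d1 | Stated rule | Delirium- and coma-free | d1/d0 against break-even |
|---|---|---|---|---|
| 40%/40% | 60%/50% | +0.42 | +0.42 | 0.83 against 1.00 |
| 40%/30% | 60%/54% | −0.13 | +0.57 | 0.90 against 0.86 |
| 50%/30% | 80%/60% | −0.14 | +1.26 | 0.75 against 0.71 |
| 40%/20% | 80%/46.2% | +0.77 | +2.17 | 0.58 against 0.75 |

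In the first row untestable days are equal and the sign is right. The last row uses an effect of the planned size: 0.338/(2√(0.631 × 0.369)) = 0.35. With c at 40% in both arms, the stated rule would give 7 × 0.60 × 0.338 = +1.42 days. The arousal difference cuts this to +0.77, which is dilution and not reversal.

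**How hard reversal is to reach.** At the planned-size ratio of 0.578, testable days must rise more than 1/0.578 = 1.73-fold, for example from 40% to above 69%. At the pilot ratio 0.2/0.9 = 0.22, reversal needs more than 1 − 0.22 = 78% untestable control days even if FAVoR has none. The pilot ratio is per patient and not per testable day, so it is only a guide.

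**Simulation.** 2,000 trials, 91 per arm, 7 days, beta-distributed variation between patients, rank-sum test at 0.05. This is not the planned chi-square test, so the results indicate scale only. In the main example the stated rule pointed the wrong way in 85% of trials, with significant benefit in 0.2% and significant harm in 18%. Delirium- and coma-free days showed significant benefit in 99%. With equal untestable days (first row), the stated rule showed significant benefit in 40% and pointed the wrong way in 5%.

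**Direction of bias, and the limit of the composite.** Take d = 50% in both arms, c0 = 30%, c1 = 20%. The stated rule gives 7 × (0.60 − 0.65) = −0.35 day; the composite gives 7 × (0.40 − 0.35) = +0.35 day. Swap the arms and both signs swap. Neither measure isolates delirium when arousal differs.

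**The case against.** Several counter-arguments have force.

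- **The rule is literally a necessary condition.** It follows the sentence on provider-documented episodes and may only mean that a chart-only episode also disqualifies a day. That is fair: the plan never says outright that a comatose day is free. But no other condition is stated, so whoever applies the text has nothing else to use.
- **Untestable days might be handled as missing under section 10.** The plan does not class them so. If it did, imputation under missing at random would assign a delirium status to an unarousable patient, which is no better. Section 18 promises a study manual that may say more, but the outcome definition belongs in the protocol.
- **Sedated to some degree is not unarousable.** Section 4 also notes a trend to lighter sedation, with most patients aware of their surroundings. This stands as a limit on size, since the rate is unknown. The same section says that many critically ill patients appear nonresponsive.
- **Sedative dose is collected and baseline imbalance is adjusted.** Dose after randomization is not a baseline covariate, and it does not enter the day count.

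A reader might infer that an arousal effect of FAVoR would generally reverse the primary result. The documents do not support that: they give no untestable-day rate, and at the pilot or planned effect dilution is likelier. Nor do scenarios with equal delirium risk in both arms show it. The two differences are then −d(c0 − c1) and +(1 − d)(c0 − c1), which have opposite signs by construction whenever c0 > c1.

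**Conclusion.** The point holds as a defect in the primary outcome definition. The stated rule cannot tell a tested-negative day from an untestable one, and followed as written it counts the latter as free. In newly ventilated, sedated patients, with a premise that includes a possible effect on consciousness, this is more than missing detail.

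The size depends on figures that the documents do not give. With equal untestable days the direction is unchanged. With unequal days the bias can run either way. Where FAVoR improves arousal, the usual result is dilution, as in the fall from +1.42 to +0.77 day. Reversal requires d1/d0 > (1 − c0)/(1 − c1), that is, a large arousal difference beside a modest delirium effect, as in the assumed case of −0.28 against +1.12 days. The conclusion also rests on the general assumption that an unarousable patient cannot score positive on the CAM-ICU.

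**What to change.** - **Outcome rule (section 9, Delirium).** State that a day counts as free only if at least one CAM-ICU was testable, no assessment or chart entry showed delirium, and the patient was not unarousable at both assessments. Fix in advance the RASS level that counts as unarousable.
- **Data capture.** Record the RASS and an unable-to-assess result, with the reason, at each 9 am and 4 pm CAM-ICU, and add both to Table 1. The reason separates days lost to arousal from days missed for logistical causes; say which of the latter are treated as missing under section 10.
- **Subjects already enrolled.** Take arousal from study forms or charted sedation scores where these exist, and report how often they do not.
- **Reporting.** Because the composite also responds to arousal alone, report delirium days, coma or untestable days, and delirium on testable days separately by arm. Keep the present count as a sensitivity analysis.

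The cost is protocol and SAP wording, added fields on the CAM-ICU form (staff already use the RASS for consent), and some chart retrieval. Fewer days will count as free. It also changes the primary outcome definition in a trial that is already enrolling, so the change should be documented, with its reason, before any unblinded analysis.
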